#### 5.3.5.11 Adverse Events Associated with an Overdose

An overdose is the accidental or intentional use of a drug in an amount higher than the dose being studied. An overdose or incorrect administration of study treatment is not itself an adverse event, but it may result in an adverse event. All adverse events associated with an overdose or incorrect administration of study drug should be recorded on the Adverse Event eCRF. If the associated adverse event fulfills serious criteria, the event should be reported to the Sponsor immediately (i.e., no more than 24 hours after learning of the event; see Section 5.4.2).

#### 5.4 IMMEDIATE REPORTING REQUIREMENTS FROM INVESTIGATOR TO SPONSOR

Certain events require immediate reporting to allow the Sponsor to take appropriate measures to address potential new risks in a clinical trial. The investigator must report such events to the Sponsor immediately; under no circumstances should reporting take place more than 24 hours after the investigator learns of the event. The following is a list of events that the investigator must report to the Sponsor within 24 hours after learning of the event, regardless of relationship to study drug:

- Serious adverse events (see Section 5.4.2 for further details)
- Non-serious adverse events of special interest (see Section 5.4.2 for further details)
- **Pregnancies** (see Section 5.4.3 for further details)

The investigator must report new significant follow-up information for these events to the Sponsor immediately (i.e., no more than 24 hours after becoming aware of the information). New significant information includes the following:

- New signs or symptoms or a change in the diagnosis
- Significant new diagnostic test results
- Change in causality based on new information
- Change in the event's outcome, including recovery
- Additional narrative information on the clinical course of the event

Investigators must also comply with local requirements for reporting serious adverse events to the local health authority and IRB/EC.

#### 5.4.2 Reporting Requirements for Serious Adverse Events and Non-Serious Adverse Events of Special Interest

For reports of serious adverse events and non-serious adverse events of special interest, investigators should record all case details that can be gathered immediately (i.e., within 24 hours) on the Adverse Event eCRF and submit the report via the electronic data capture (EDC) system. A report will be generated and sent to the Sponsor's Safety Risk Management department by the EDC system.

In the event that the EDC system is unavailable, a paper Serious Adverse Event/Non-Serious Adverse Event of Special Interest CRF and Fax Coversheet should be completed and faxed to Safety Risk Management or its designee immediately (i.e., no more than 24 hours after learning of the event), using the fax numbers provided below. Once the EDC system is available, all information will need to be entered and submitted via the EDC system. *Instructions for reporting post-study adverse events are provided in Section 5.6.* 

For Sites in U.S. and Canada:
Fax No.:
For Sites in France:
Fax No.:
For Sites in Germany:
Fax No.:
Alternate Fax No.: (pause)
For Sites in Spain:
Fax No.:
For Sites in United Kingdom:
Fax No.:

Relevant follow-up information should be submitted to Genentech's Drug Safety Department or its designee as soon as it becomes available and/or upon request.

# 5.4.3 Reporting Requirements for Pregnancies

# 5.4.3.1 Pregnancies in Female Patients

Female patients of childbearing potential will be instructed to immediately inform the investigator if they become pregnant during the study or within *8 weeks* after the last dose of study drug. A Pregnancy Report eCRF should be completed by the investigator immediately (i.e., no more than 24 hours after learning of the pregnancy) and submitted via the EDC system. A pregnancy report will automatically be generated and sent to Safety Risk Management. Pregnancy should not be recorded on the Adverse Event eCRF. The investigator should discontinue study drug and counsel the patient, discussing the risks of the pregnancy and the possible effects on the fetus. Monitoring of the patient should continue until conclusion of the pregnancy.

In the event that the EDC system is unavailable, a Pregnancy Report worksheet and Pregnancy Fax Coversheet should be completed and faxed to Safety Risk Management or its designee immediately (i.e., no more than 24 hours after learning of the pregnancy), using the fax numbers provided in Section 5.4.2.

# 5.4.3.2 Pregnancies in Female Partners of Male Patients

Male patients will be instructed through the Informed Consent Form to immediately inform the investigator if their partner becomes pregnant during the study or within *8 weeks* after the last dose of study drug. A Pregnancy Report eCRF should be completed by the investigator immediately (i.e., no more than 24 hours after learning of the pregnancy) and submitted via the EDC system. Attempts should be made to collect and report details of the course and outcome of any pregnancy in the partner of a male patient exposed to study drug. The pregnant partner will need to sign an Authorization for Use and Disclosure of Pregnancy Health Information to allow for follow-up on her

pregnancy. Once the authorization has been signed, the investigator will update the Pregnancy Report eCRF with additional information on the course and outcome of the pregnancy. An investigator who is contacted by the male patient or his pregnant partner may provide information on the risks of the pregnancy and the possible effects on the fetus, to support an informed decision in cooperation with the treating physician and/or obstetrician.

In the event that the EDC system is unavailable, follow reporting instructions provided in Section 5.4.3.1.

# 5.4.3.3 Abortions

Any spontaneous abortion should be classified as a serious adverse event (as the Sponsor considers spontaneous abortions to be medically significant events), recorded on the Adverse Event eCRF, and reported to the Sponsor immediately (i.e., no more than 24 hours after learning of the event; see Section 5.4.2).

# 5.4.3.4 Congenital Anomalies/Birth Defects

Any congenital anomaly/birth defect in a child born to a female patient exposed to study drug or the female partner of a male patient exposed to study drug should be classified as a serious adverse event, recorded on the Adverse Event eCRF, and reported to the Sponsor immediately (i.e., no more than 24 hours after learning of the event; see Section 5.4.2).

# 5.5 FOLLOW-UP OF PATIENTS AFTER ADVERSE EVENTS

# 5.5.1 Investigator Follow-Up

The investigator should follow each adverse event until the event has resolved to baseline grade or better, the event is assessed as stable by the investigator, the patient is lost to follow up, or the patient withdraws consent. Every effort should be made to follow all serious adverse events considered to be related to study drug or trial-related procedures until a final outcome can be reported.

During the study period, resolution of adverse events (with dates) should be documented on the Adverse Event eCRF and in the patient's medical record to facilitate source data verification. If, after follow-up, return to baseline status or stabilization cannot be established, an explanation should be recorded on the Adverse Event eCRF.

All pregnancies reported during the study should be followed until pregnancy outcome. If the EDC system is not available at the time of pregnancy outcome, follow reporting instructions provided in Section 5.4.3.1.

# 5.5.2 Sponsor Follow-Up

For serious adverse events, non-serious adverse events of special interest, and pregnancies, the Sponsor or a designee may follow up by telephone, fax, electronic mail, and/or a monitoring visit to obtain additional case details and outcome information

Crenezumab—Genentech, Inc. 70/Protocol GN28525, Version 6

(e.g., from hospital discharge summaries, consultant reports, autopsy reports) in order to perform an independent medical assessment of the reported case.

# 5.6 POST-STUDY ADVERSE EVENTS

At the time of study completion or study discontinuation, the investigator should instruct each patient to report to the investigator any subsequent adverse events that the patient's personal physician believes could be related to prior study drug treatment or study procedures.

The investigator should notify the Sponsor of any death, serious adverse event, or other adverse event of concern occurring at any time after a patient has discontinued study participation if the event is believed to be related to prior study drug treatment. The Sponsor should also be notified if the investigator becomes aware of the development of cancer or a congenital anomaly/birth defect in a subsequently conceived offspring of a female patient exposed to study drug or the female partner of a male patient exposed to study drug.

The investigator should report these events directly to Safety Risk Management via *fax* machine using the Serious Adverse Event Reporting Form and fax cover sheet as follows:

#### 5.7 EXPEDITED REPORTING TO HEALTH AUTHORITIES, INVESTIGATORS, INSTITUTIONAL REVIEW BOARDS, AND ETHICS COMMITTEES

The Sponsor will promptly evaluate all serious adverse events and non-serious adverse events of special interest against cumulative product experience to identify and expeditiously communicate possible new safety findings to investigators, IRBs, ECs, and applicable health authorities based on applicable legislation.

Crenezumab—Genentech, Inc. 71/Protocol GN28525, Version 6 To determine reporting requirements for single adverse event cases, the Sponsor will assess the expectedness of these events using the following reference document: Crenezumab Investigator's Brochure

The Sponsor will compare the severity of each event and the cumulative event frequency reported for the study with the severity and frequency reported in the applicable reference document.

Reporting requirements will also be based on the investigator's assessment of causality and seriousness, with allowance for upgrading by the Sponsor as needed.

# 6. STATISTICAL CONSIDERATIONS AND ANALYSIS PLAN

# 6.1 DETERMINATION OF SAMPLE SIZE

This study is open to all patients who completed Study ABE4869g or ABE4955g and who met the eligibility criteria. Accordingly, the sample size for this study is not based on a formal sample size calculation.

# 6.2 SUMMARIES OF CONDUCT OF STUDY

The number of patients who enroll, discontinue (early discontinuation of treatment or early termination from the study), and complete the study (through Week 153) will be tabulated by treatment group. Reasons for early discontinuation of treatment or early termination from the study will be listed and summarized by treatment group. Any eligibility criteria exceptions and other protocol deviations will also be summarized by treatment group

# 6.3 SUMMARIES OF TREATMENT GROUP COMPARABILITY

Demographic and baseline characteristics such as age, sex, race, *ApoE4* status, and baseline MMSE and group assignment in Study ABE4869g and ABE4955g will be summarized for all enrolled patients by use of descriptive statistics.

# 6.4 SAFETY ANALYSES

The safety analyses will include all enrolled patients who received at least one dose of study drug in this OLE study following their completion of Study ABE4869g or ABE4955g.

These patients will be grouped based on treatment assignment in the OLE study and Study ABE4869g or ABE4955g. Primary safety analysis will be performed after enrolled patients have completed Week *153* visit of the OLE study.

Safety will be assessed by monitoring adverse events, clinical laboratory evaluations, MRI evaluations, and immunogenicity as measured by ATAs. Patients will be analyzed according to actual treatment received.

# 6.4.1 Adverse Events

Adverse events will be recorded from the time informed consent is given until a patient completes the study or discontinues prematurely. Adverse events reported during the screening period, the 144-week treatment period, and the 8-week follow-up period will be summarized separately. Verbatim descriptions of adverse events will be coded and analyzed using appropriate thesaurus terms. A treatment-emergent adverse event is defined as any adverse event reported during or after the first dose of study drug.

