The study consists of three periods: a screening period (up to 14 days), the window between the last dose in ABBY/BLAZE and the first dose in OLE may last 6 weeks, but may be prolonged on a case by case basis for relevant clinical, administrative, or operational reasons (these reasons must be discussed with the medical monitor in advance of screening; if necessary, some screening procedures may need to be repeated); a treatment period of 144 weeks (Week 1 [Day 1] to Week 145), and an 8-week safety follow-up period (Weeks 145 to 153). The final safety analysis will be performed at 153 weeks. The original GN28525 protocol included a treatment period of 92 weeks (Week 1 [Day 1] to Week 93). Version 6 of the GN28525 protocol expands this treatment period by 52 weeks (13 additional IV doses from Week 97 to Week 145). Patients who are still enrolled in Study GN28525 may enter the additional OLE treatment period (Week 145) if they have not discontinued treatment for

Crenezumab—Genentech, Inc. 39/Protocol GN28525, Version 6

[figure not shown]
safety reasons. Patients who have already completed or discontinued from Study GN28525 are not eligible to receive additional treatment from Week 97 to Week 145.

The Week 73 assessment (including MRI) of Studies ABE4869g and ABE4955g will be used to determine the patient's eligibility in this OLE trial. Data from the Week 73 visit assessments in Studies ABE4869g and ABE4955g will be extracted and incorporated in the OLE screening datasets. Patients participating in this OLE study must be enrolled (i.e., Day 1 of the OLE treatment period) no later than 14 days after completion of the Week 73 assessments (including MRI) of Study ABE4869g or ABE4955g, except for individual exceptions, determined on a case by case basis, as mentioned above.

The first dose of crenezumab is administered on Day 1 of the treatment period, and the last dose of treatment is at Week 145. After patients complete the 144-week treatment period, they will enter the follow-up period. Patients who are prematurely discontinued from the OLE study treatment will also discontinue from the OLE study and will be followed for safety for 8 weeks after their last dose of crenezumab.

Patients will remain blinded to their assignment in Study ABE4869g or ABE4955g, and investigators are not permitted to provide treatment assignment in ABE4869g or ABE4955g until permitted by the Sponsor.

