#### 5.3.1 Adverse Event Reporting Period

Investigators will seek information on adverse events at each patient contact. All adverse events, whether reported by the patient or noted by study personnel, will be recorded in the patient's medical record and on the Adverse Event eCRF.

Adverse events occurring after informed consent has been obtained but prior to initiation of study drug, only serious adverse events caused by a protocol-mandated intervention should be reported (e.g., serious adverse events related to invasive procedures such as biopsies). No events during the screening period should be entered into the Adverse Event eCRF; they should be captured in the original study AE CRF (i.e., Abby or Blaze), if within the reported period for those.

Only adverse events and serious adverse events that are unresolved when the patient is randomized (on Day 1) in Study GN28525 should be carefully recorded over to the GN28525 eCRF Database.

**After initiation of study drug**, all adverse events and serious adverse events, regardless of relationship to study drug, will be reported until at least *8 weeks* after the last dose of study drug. After this period, investigators should report any deaths, serious adverse events, or other adverse events of special interest (see Section 5.6).

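### Section 6.4.1 promises a separate screening-period adverse event summary, but the recording rule in Section 5.3.1 leaves it incomplete and selective

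*Combined protocol and SAP*

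**What the plan says.** The analysis section, 6.4.1, makes two commitments. On collection: "Adverse events will be recorded from the time informed consent is given until a patient completes the study or discontinues prematurely". On reporting: "Adverse events reported during the screening period, the 144-week treatment period, and the 8-week follow-up period will be summarized separately". It then defines a treatment-emergent event by when the event is reported relative to the first dose, not by when it began.

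The collection section, 5.3.1, gives sites a different instruction: "No events during the screening period should be entered into the Adverse Event eCRF; they should be captured in the original study AE CRF", with the condition "if within the reported period for those". It makes two allowances. Before the first dose, "only serious adverse events caused by a protocol-mandated intervention should be reported". Events still unresolved on Day 1 are copied into the OLE database.

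Section 5.4.2 sets the route for serious events: investigators are to "record all case details that can be gathered immediately (i.e., within 24 hours) on the Adverse Event eCRF". A paper form is offered only when the electronic system is down.

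Section 3.1.1 gives a usual window of 6 weeks between the last feeder dose and the first OLE dose, which "may be prolonged on a case by case basis for relevant clinical, administrative, or operational reasons". No maximum is given. The same section says that feeder Week 73 visit assessments will be brought into the OLE screening datasets. It does not mention feeder adverse event records.

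**The concern.** The analysis section plans a table that the collection section does not supply. Three things follow for a study whose primary objective is long-term safety.

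- **Selective content.** A screening table drawn from the OLE data would favour events that persist to Day 1 and serious events tied to a procedure. Short, self-limiting events would be absent because of the recording rule. A reader could take a sparse table to mean that little happened.
- **Leakage into the treatment period.** An event that began before Day 1 and is entered on or after first dosing meets the literal definition of treatment-emergent. Section 2.2 names treatment-emergent events as a focus of the safety objective, so the misclassification would reach a main output.
- **Unclear reporting route.** A site with a screening serious event caused by a study procedure must report it within 24 hours, normally on a form that Section 5.3.1 closes to screening events.

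There is also a conditional risk. If a prolonged gap outlasts the feeder reporting period, an event that starts and resolves inside the uncovered interval belongs to neither adverse event database.

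**Working it through.** **Step 1. Where each kind of screening-period event goes.** Applying Sections 5.3.1, 5.4.2 and 6.4.1 literally:

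| Event with onset before Day 1 | Feeder CRF | OLE database | Status in the 6.4.1 summaries |
|---|---|---|---|
| Resolves before Day 1, feeder period open | Yes | No | No named transfer, so not available |
| Resolves before Day 1, feeder period closed | No | No | Missing from both |
| Unresolved on Day 1 | If period open | Yes, carried over | Screening by onset, but treatment-emergent if entered on or after first dose |
| Serious, caused by a protocol-mandated intervention | If period open | Must be reported, but 5.3.1 bars the eCRF that 5.4.2 uses | Route unclear |

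Only the last two rows offer a route into OLE data. The table is therefore incomplete and selective, but not necessarily empty.

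**Step 2. Reproduce the usual gap.** Section 1.3 puts the last feeder dose on the first day of Week 69 and the final efficacy assessments at Week 73. Section 3.1.1 requires Day 1 within 14 days of the Week 73 assessments, apart from exceptions.

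(73 − 69) weeks + 14 days = 4 + 2 = 6 weeks, which agrees with the 6-week window in Section 3.1.1.

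**Step 3. Range for the uncovered interval.** Let G be the weeks from last feeder dose to OLE Day 1, and R the feeder adverse event reporting period in weeks after last dose. R is not in the documents, so it is assumed over a range; R = 4 would mean that reporting closed at Week 73. Values of G above 6 are also assumptions, because the prolongation has no stated limit.

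Uncovered weeks = max(0, G − R)

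| G (weeks) | R = 4 | R = 8 | R = 12 | R = 16 |
|---|---|---|---|---|
| 6 | 2 | 0 | 0 | 0 |
| 8 | 4 | 0 | 0 | 0 |
| 10 | 6 | 2 | 0 | 0 |
| 12 | 8 | 4 | 0 | 0 |
| 16 | 12 | 8 | 4 | 0 |

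These are weeks per patient, not events. The documents give neither the number of patients with prolonged gaps nor an event rate for the interval, so no event count can be derived.

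**Step 4. How many patients a prospective change could reach.** Section 1.3.3.5 reports serious events as of 27 May 2014 in 15 SC patients (10.1%) and 18 IV patients (8.5%).

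15 / 0.101 ≈ 149 and 18 / 0.085 ≈ 212, together about 360.

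Section 9.3 expects about 390 participants. Most had therefore passed screening by that date.

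**The case against.** The strongest reply is that most screening-period events are recorded somewhere. Section 5.3.1 sends them to the feeder CRF while that period is open, and Section 6.4.1 does not say that the screening summary must come from the OLE eCRF. A feeder period of 8 weeks or more after last dose would cover the usual gap completely. There is indirect support for follow-up past Week 73: dosing in ABE4869g ended on 29 October 2013 (Section 1.3.1) and the study was completed in May 2014 (Section 1.3), about 26 to 31 weeks later. The medical history in Section 4.3.2 may also pick up a significant illness in the gap. Finally, the primary adverse event outcomes in Section 3.4.1 cover the treatment period only.

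Much of this stands. A reader might infer that the screening table must be empty; feeder capture and the two allowances in Section 5.3.1 rule that out. The completion date suggests a longer feeder period but does not establish it for patients who rolled over. Medical history is not an adverse event record. The intervention-related rule comes just before the bar in Section 5.3.1 and can be read as an exception to it, so that conflict is narrow, though the text should say so.

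The reply does not supply a data source for the promised summary. Nor does it answer the treatment-emergent definition, which acts within the treatment period itself.

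**Conclusion.** The contradiction is in the current text and should be corrected before the Week 153 analysis. Sections 5.3.1 and 6.4.1 disagree on whether this study records screening-period events. No transfer of feeder adverse event records is named, and carried-over events can be misclassified as treatment-emergent. The effect on the primary adverse event outcomes is limited to that misclassification.

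Loss to both studies is a conditional finding. It needs a gap longer than the feeder reporting period and an event that resolves before Day 1 and is not an intervention-related serious event. Under the assumed range it runs from 0 to 2 weeks for the usual gap and 0 to 12 weeks for a 16-week gap. The true size cannot be computed.

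Two stronger readings are not supported:

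- **Gaps are longest in patients delayed for clinical reasons.** Section 3.1.1 lists clinical, administrative and operational reasons together and gives no durations.
- **Residual drug measures the harm.** With the single-dose half-life of 17 to 26 days in Section 1.3.4 and simple one-phase decay, 0.5^(42/17) = 0.18 to 0.5^(42/26) = 0.33 of the concentration remains at 42 days. This says nothing about how many events go unrecorded.

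**What to change.** - **Reconcile Sections 5.3.1, 5.4.2 and 6.4.1.** State whether screening-period events are collected, in which database and over which dates.
- **Give the screening summary a source, or delete it.** If kept, build it from feeder adverse event records dated from OLE consent or Week 73 to Day 1, plus the events carried over on Day 1.
- **Classify by onset date.** Apply this to carried-over events, so that those which began before Day 1 are not counted as treatment-emergent merely because they were entered later.
- **State the exception.** Say that intervention-related screening serious events may be entered on the Adverse Event eCRF despite the general bar.
- **Deal with prolonged gaps.** State the feeder reporting period. For patients whose gap exceeded it, add events from existing source records, or report the interval as not covered.

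The cost is wording in three sections, a date-limited extract from the feeder data and limited retrospective entry for patients with prolonged gaps. A new eCRF flag for future screenings would add little, since about 360 of about 390 expected patients were already enrolled by May 2014. No dose, visit or sample size changes.

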# 4.3.3 Physical Examinations

A complete physical examination should include an evaluation of the head, eyes, ears, nose, and throat and the cardiovascular, dermatological, musculoskeletal, respiratory, and gastrointestinal systems. Any abnormality identified at baseline should be recorded on the General Medical History and Baseline Conditions eCRF.

At subsequent visits (or as clinically indicated), changes from baseline abnormalities should be recorded in patient notes. New or worsened clinically significant abnormalities should be recorded as adverse events on the Adverse Event eCRF.

Crenezumab—Genentech, Inc. 49/Protocol GN28525, Version 6

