#### 5.2.1 Adverse Events

According to the ICH guideline for Good Clinical Practice, an adverse event is any untoward medical occurrence in a clinical investigation patient administered a pharmaceutical product, regardless of causal attribution. An adverse event can therefore be any of the following:

- Any unfavorable and unintended sign (including an abnormal laboratory finding), symptom, or disease temporally associated with the use of a medicinal product, whether or not considered related to the medicinal product
- Any new disease or exacerbation of an existing disease (a worsening in the character, frequency, or severity of a known condition), except as described in Section 5.3.5.9
- Recurrence of an intermittent medical condition (e.g., headache) not present at baseline
- Any deterioration in a laboratory value or other clinical test (e.g., ECG, X-ray) that is associated with symptoms or leads to a change in study treatment or concomitant treatment or discontinuation from study drug

Crenezumab—Genentech, Inc. 58/Protocol GN28525, Version 6

• Adverse events that are related to a protocol-mandated intervention, including those that occur prior to assignment of study treatment (e.g., screening invasive procedures such as biopsies)

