# 5.3.5.8 Pre-Existing Medical Conditions

A pre-existing medical condition is one that is present at the screening visit for this study. Such conditions should be recorded on the General Medical History and Baseline Conditions eCRF.

A preexisting medical condition should be recorded as an adverse event only if the frequency, severity, or character of the condition worsens during the study. When recording such events on the Adverse Event eCRF, it is important to convey the concept that the preexisting condition has changed by including applicable descriptors (e.g., "more frequent headaches").

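### Section 6.4.1 defines a treatment-emergent adverse event by when it is reported, with no onset or worsening criterion, so feeder-study events carried over on Day 1 can be counted as emergent on extension crenezumab

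*Combined protocol and SAP*

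**What the plan says.** Section 6.4.1 (Adverse Events) gives the only definition in the supplied text: "A treatment-emergent adverse event is defined as any adverse event reported during or after the first dose of study drug". It also promises separate summaries of adverse events for the screening, treatment and follow-up periods.

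Section 5.3.1 (Adverse Event Reporting Period) deals with events that straddle the two studies. Its carry-over rule covers feeder-study events, whether serious or not, and reads: "that are unresolved when the patient is randomized (on Day 1) in Study GN28525 should be carefully recorded over to the GN28525 eCRF Database". For the time before dosing it says: "No events during the screening period should be entered into the Adverse Event eCRF". Those events go to the feeder study's own adverse event form, if they fall within that study's reporting period.

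Section 3.1.1 fixes the timing: "The first dose of crenezumab is administered on Day 1 of the treatment period".

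Two other rules bear on the point. Section 5.3.5.8 sends a condition present at the screening visit to the medical history and baseline conditions form, and makes it an adverse event only "if the frequency, severity, or character of the condition worsens during the study". Section 5.3.5.3 has a persistent event recorded once, with a new record if it becomes more severe or becomes serious.

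**The concern.** In a rollover study, the treatment-emergent rule has to separate what began before the extension from what began or worsened in it. A rule based on the time of reporting does not do that. Old events enter the new database on the same day that the rule starts to count, and nothing in 6.4.1 excludes them.

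Treatment-emergent adverse events are named first in the safety objective (Section 2.2), and the frequency of adverse events is a primary outcome (Section 3.4.1). Section 6.4 groups patients by extension and feeder assignment. The former placebo patients form the group in which new and old events most need to be told apart, because an event that began on placebo would appear there as emergent on crenezumab. What is at stake is inflated or inconsistently counted incidence. No hypothesis test depends on it.

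**Working it through.** There is no planned figure to reproduce: Section 6.1 states that the sample size has no formal basis. The check is mainly textual, followed by the weight of one patient.

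**The texts side by side**

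1. *Trigger.* Section 6.4.1 counts an event if it is reported at or after the first dose. Onset date, baseline status and worsening do not appear.
2. *Carry-over.* Section 5.3.1 moves unresolved feeder events into the extension database as of Day 1 and still calls them adverse events. It refers to the eCRF database and does not say whether they go on the adverse event form or the medical history form.
3. *Timing.* Day 1 is the first dosing day (Section 3.1.1). Whether the carry-over entry is made before or after the infusion is not specified.
4. *Result.* An unchanged event that began in a feeder study meets the literal 6.4.1 rule if the carry-over entry counts as a report. An event with onset before Day 1 that is first mentioned at a later visit meets it in any case.
5. *Possible limits.* Sections 5.3.5.3 and 5.3.5.8 govern what sites write down, and 6.4.1 cites neither. In Section 5.2.1, new or exacerbated disease is one of several alternative ways to qualify as an adverse event, so it does not narrow the definition.

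Two programmers could follow this text faithfully and produce different tables.

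**Weight of one miscounted patient**

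Section 1.3.3.5 gives counts and percentages for the extension as of 27 May 2014, but no denominators. They can be recovered by finding each N for which count/N rounds to every printed percentage.

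| Group | Counts and printed percentages | N that fits all |
|---|---|---|
| SC | 15 = 10.1%, 8 = 5.4%, 6 = 4.1%, 1 = 0.7% | 148 |
| IV | 18 = 8.5%, 2 = 0.9%, 3 = 1.4%, 1 = 0.5% | 211 to 213 |

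Check for SC: 15/148 = 10.14% and 6/148 = 4.05%, which both round as printed; 15/147 = 10.20% and 6/149 = 4.03% do not. For IV: 18/211 = 8.53% and 18/213 = 8.45% fit; 18/210 = 8.57% and 18/214 = 8.41% do not.

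The total is 148 + 211 = 359 to 148 + 213 = 361; take 360. One extra patient then adds:

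- SC: 1/148 = 0.68 points
- IV: 1/212 = 0.47 points
- Overall: 1/360 = 0.28 points

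If k patients are miscounted for a term, and none of them also has a true new event of that term, overall incidence rises by k × 0.28 points. The documents do not give k.

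**Screening-period summary**

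Section 6.4.1 plans a summary of screening-period events, while Section 5.3.1 keeps those events off the extension's adverse event form. The summary therefore has to come from the feeder-study forms, which 6.4.1 does not name.

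**The case against.** The best defence is that the protocol, read as a whole, already handles this. A feeder event still present at extension screening fits the definition of a pre-existing condition in Section 5.3.5.8, so it belongs in medical history unless it worsens. Section 5.3.1 speaks of recording such events over to the database but of reporting events after dosing starts, and reporting is the word that 6.4.1 uses. On that reading, unchanged carried-over events are never counted. Former placebo patients are also shown separately, and the summaries are descriptive.

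This reading is plausible, and it is why miscounting cannot be asserted as fact. But it has to be assembled by the reader. Section 5.3.1 calls the carried-over events adverse events and names no form, and 6.4.1 does not adopt the worsening rule. The reading also leaves open the event with onset before Day 1 that is first reported later.

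A reader might go further and infer that the incidence of cerebral microhemorrhage in the extension would be overstated, since it was a common feeder-study event and up to eight lesions are allowed at entry. The documents do not support that. The incidence of ARIA-H is a separate outcome in Section 3.4.1, read centrally from MRI and summarized under Section 6.4.3. Section 1.3.3.5 already reports incident microhemorrhages. A projection would also need the number of feeder patients who rolled over with that event unresolved, which is not given.

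**Conclusion.** The concern holds as a fault in a stated rule. Read literally, 6.4.1 allows events that began before the extension to be counted as treatment-emergent in it, and no text that it cites prevents this. Whether such counting would happen, and how often, cannot be determined from the documents. A reader might conclude that the incidence in the extension is in fact inflated; that is not shown.

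The only size that follows from the plan's figures is the weight per patient: about 0.28 points overall, 0.68 in the SC group and 0.47 in the IV group. These weights rest on denominators inferred from rounded percentages at 27 May 2014. Finer grouping by feeder assignment would make each patient weigh more.

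One limit remains. Section 6.7 refers to a separate Statistical Analysis Plan, for the exploratory objectives only. It is not in the supplied text, so a fuller definition there cannot be ruled out.

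**What to change.** Replace the definition in 6.4.1 with: *A treatment-emergent adverse event is an adverse event with onset on or after the first OLE dose, or a pre-existing event that worsens in frequency, severity, seriousness or character on or after that dose.* Including frequency and character matches Sections 5.2.1 and 5.3.5.8.

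Add that events carried over from ABE4869g or ABE4955g, identified by a start date before the first OLE dose, are listed separately by feeder treatment and are not counted unless they worsen. The new record that Section 5.3.5.3 requires identifies an increase in severity or seriousness.

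Name the feeder-study adverse event forms as the source of the screening-period summary, or delete that summary.

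The cost is a change of wording and a small derivation, with no change to what sites record. The derivation does assume that sites entered the true start date of carried-over events. Two consequences should be accepted openly: the treatment-emergent count may fall slightly, and unchanged events that began on feeder crenezumab will appear only in the separate listing.
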